# Statistical Analysis Plan:

Primary endpoint analysis:

- Univariate X analysis for categorical variables to investigate *Courses of antibiotic treatment*.
- Univariate X analysis for categorical variables to investigate *Number of hospitalisations*.
- Student t testing will be used to analyse *nocturnal oxygenation and ventilation outcomes* comparing one year before and after starting treatment with Hypertonic Saline.
- Independent t testing and Mann-Whitney U test to analyse *Rate of decline in pulmonary function*.
- Cox proportional hazard model to test differences in primary endpoints *for different baseline*

Secondary enpoint analysis:

- Univarate analysis to analyse *Ease of airway clearance*.
- Univariate analysis on **perception of treatment**.

Data and all appropriate documentation will be stored for a minimum of 10 years after the completion of the study, including the follow-up period.

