## Secondary Objectives:

- Assess the effect of the treatment with nebulised hypertonic saline in children and young people with Neuromuscular disease or Cerebral Palsy on the number of courses of antibiotic prescribed compared to year before starting treatment.
- Determine whether the use of nebulised Hypertonic Saline in children and young people with Neuromuscular Disease or Cerebral Palsy reduces the frequency of hospitalisations due to respiratory exacerbations compared to year before commencing treatment.
- Explore the impact of the treatment with hypertonic saline on nocturnal oxygenation and ventilation in children and young people with Neuromuscular disease or with Cerebral Palsy.
- Evaluate whether the treatment with nebulised hypertonic saline in children and young people with neuromuscular disease or cerebral palsy improves the ease of airway clearance.
- In the subgroup of participants with neuromuscular disease who can perform spirometry, assess whether the use of Hypertonic Saline decreases rate of decline of pulmonary function compared to year before commencing treatment.
- Explore how parents of children and young people with Neuromuscular disease or with Cerebral Palsy perceive the treatment with nebulised hypertonic saline compared to previous management.

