#### 3.1 STUDY OUTCOME MEASURES

**Primary Endpoints:** 

- Number of respiratory exacerbations requiring antibiotic treatment.
- Number of hospitalsiations due to respiratory exacerbations, using NHANES 2011 questionnaire for Hospitalisation and access to care HUQ.010.
- Nocturnal oximetry and polygraphy outcomes: Basal SpO2 (%), Minimum SpO2 (%), Maximum SpO2 (%), Average SpO2 (%), Oxygen desaturation index (ODI), Snoring and End tidal CO2 (EtCO2).
- Rate of decline of pulmonary function.

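### Antibiotic courses and hospitalisations are before/after counts, but the SAP gives each only a chi-square for categorical variables, with no comparison, categories, pairing or effect estimate

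*Combined protocol and SAP*

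**What the plan says.** Section 3.1 lists four primary endpoint bullets. The first is "Number of respiratory exacerbations requiring antibiotic treatment". The second is the number of respiratory hospitalisations, "using NHANES 2011 questionnaire for Hospitalisation and access to care HUQ.010". Both are counts per child.

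The secondary objectives in Section 2 give the comparison. For antibiotics, the effect is to be assessed "on the number of courses of antibiotic prescribed compared to year before starting treatment". For admissions, the question is whether treatment "reduces the frequency of hospitalisations due to respiratory exacerbations compared to year before commencing treatment". Sections 3 and 4.2 admit only children with 12 months or more on treatment, and no untreated group is described.

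The Statistical Analysis Plan in Section 6 then gives one line to each endpoint: "Univariate X 2 analysis for categorical variables to investigate *Courses of antibiotic treatment" and "Univariate X 2 analysis for categorical variables to investigate *Number of hospitalisations". The next line, on nocturnal outcomes, does name its contrast: "comparing one year before and after starting treatment with Hypertonic Saline". One further line covers all primary endpoints: "Cox proportional hazard model to test differences in primary endpoints *for different baseline".

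**The concern.** The objectives ask whether each child has fewer events in the year after starting than in the year before. A chi-square for categorical variables does not answer that. The counts must first be cut into categories, and none are given. A Pearson test on period by category treats the two years of one child as two different children. No reading of the line yields a size of change.

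The Cox line does not fill the gap. It concerns differences by baseline, no time-to-event outcome is defined anywhere, and it is not a paired method for counts.

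At stake is the analysis of two of the four primary endpoint bullets. As written, the analyst would choose the comparison and the cut-points after seeing the data. Depending on that choice, the test could be conservative and weak, or could reject too often.

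Two inputs are also unsettled:

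- The antibiotic outcome is exacerbations in Section 3.1 but courses in Section 2 and the SAP.
- Admissions are tied to HUQ.010 in Section 3.1, while Section 3 describes a chart review. The documents give neither the wording nor the recall period of HUQ.010.

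**Working it through.** **1. Text side by side**

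| Element | Objectives and endpoints | SAP line |
|---|---|---|
| Variable | Count | Categorical; no categories given |
| Contrast | Against the year before treatment | None stated |
| Structure | Same child in both periods | No pairing |
| Result | Reduction in number or frequency | No estimate or interval |

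**2. The plan's own figure.** Section 6 aims for 40 participants per group because the study is a pilot. It gives no alpha, power, effect, rate or dispersion, so 40 cannot be reproduced. This point does not depend on it.

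**3. Assumptions for the illustration.** None of these is in the documents.

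- 40 children; mean 3 (or 0.5) events a year before treatment.
- Child-level rates gamma with shape 1.5; Poisson counts given the rate.
- Lognormal year-to-year variation within child, CV 0, 0.5 or 0.8.
- Rate ratio 0.7 for power and 1.0 for size; two-sided 5%.
- 20,000 simulated studies per scenario, so the simulation standard error is at most √(0.25/20,000) = 0.35 percentage points.

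**4. The mechanism by hand (CV 0, 3 events a year).** P(0) = (1.5/(1.5+μ))^1.5.

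- *Information lost.* P(0) is (1.5/4.5)^1.5 = 0.192 before and (1.5/3.6)^1.5 = 0.269 after. Children with any event fall from 40 × 0.808 = 32.3 to 40 × 0.731 = 29.2, while total events fall from 120 to 84. A 30% reduction shows as about three children.
- *Pairing ignored.* With no effect, P(0 in both years) = (1.5/7.5)^1.5 = 0.0894. The within-child correlation is (0.0894 − 0.192²)/(0.192 × 0.808) ≈ 0.34. The unpaired variance is too large by 1/(1 − 0.34), so the true size is about P(|Z| > 1.96/√0.66) ≈ 1.6% (simulated 1.9%).
- *Event totals.* A chi-square on the two totals assumes pure Poisson variation. Year-to-year CV inflates the variance by 1 + μ·E[g²]·CV², where g is the child's rate relative to the mean and E[g²] = 1 + 1/1.5 = 1.67. At CV 0.5 this is 1 + 3 × 1.67 × 0.25 = 2.25, giving size P(|Z| > 1.96/1.5) ≈ 19% (simulated 18%).

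**5. Simulation results (CV 0 / 0.5 / 0.8)**

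| Scenario | Chi-square 0/1-2/3+ | Wilcoxon signed-rank |
|---|---|---|
| Size, n=40, 3/year | 2 / 2 / 3% | 5 / 5 / 5% |
| Power, n=40, 3/year | 11 / 10 / 10% | 65 / 41 / 28% |
| Power, n=40, 0.5/year | 6 / 6 / 6% | 16 / 14 / 13% |
| Power, n=20, 3/year | 5 / 6 / 6% | 35 / 22 / 15% |
| Power, n=80, 3/year | 26 / 22 / 19% | 92 / 70 / 52% |

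The rows for 20 and 80 children are shown because the target of 40 per group counts parents as well as children, and the groups are not defined. Over four category schemes (any/none; 0/1-2/3+; 0-1/2-3/4+; 0/1/2/3+), with 40 children at 3 a year, chi-square power is 8-12% and size 1-3%. The event-total chi-square has size 5 / 18 / 32%.

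A plainer model (no year-to-year variation; 1 or 3 events a year; frailty variance 0.5 or 1.0; rate ratio 0.6 or 0.7) gives the same ordering: chi-square power 5-35%, paired rate ratio 29-92%.

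**6. What an estimate would add.** With totals A after and B before, the rate ratio is A/B, with SE(log) = (n/(n−1))·√Σ(aᵢ/A − bᵢ/B)² and t on n−1 df. The median 95% CI at a true ratio of 0.7 is:

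- 3/year: 0.53-0.93, 0.47-1.04, 0.43-1.15.
- 0.5/year: 0.34-1.41, 0.33-1.48, 0.31-1.58.

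**7. Courses or exacerbations.** If 30% of exacerbations needed a second course (assumed), the course total is 30% higher. At 3 exacerbations a year and CV 0, Wilcoxon power on courses is then 59% rather than 65%.

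**The case against.** The SAP never says the chi-square is unpaired; McNemar's test is also a chi-square. Under the same assumptions, McNemar on any/none has size of about 4-5%. Its power is 15%, 13% and 12% at 3 events a year and 12%, 11% and 11% at 0.5. That removes the conservatism and nearly matches Wilcoxon at the low rate. At 3 a year it remains far behind, because the counts are still discarded. It also needs a stated cut-point and pairing, and neither is given.

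The power argument is uneven. If admissions are infrequent, a real reduction would probably be missed after the fix too; at 3 a year Wilcoxon has below 50% power at CV 0.5 and 0.8. This stands. What holds across scenarios is the missing estimate and the missing pre-set categories.

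The study calls itself a pilot and its primary objective is exploratory; the counts could be re-analysed from the same charts. That lowers the stakes. However, Section 1.2 states a directional hypothesis, Section 3.1 makes both endpoints primary, and a pilot mainly needs an estimate with an interval.

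Some side points are softer. Section 3 mentions two parent questionnaires and only one parent form is visible. That form asks about antibiotic courses and doctor visits, so HUQ.010 may be the other. The request is therefore only to state the source.

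**Conclusion.** The concern holds and must be fixed. For two of the four primary endpoint bullets, the stated method does not match the stated within-child comparison of counts. This conclusion rests on the text alone.

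The simulated figures show direction and rough size under assumed rates and dispersion. At 3 events a year, category-based chi-square readings (Pearson or McNemar) reach 8-15% power with 40 children, against 28-65% for a paired count test. The event-total reading can reach 32% false positives. At 0.5 events a year the power gain is small. On any reading, the plan reports no size of change.

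**What to change.** In the SAP, replace both chi-square lines with a within-child comparison of the 12 months before and the 12 months after starting treatment:

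- **Test:** Wilcoxon signed-rank on the within-child difference in counts.
- **Estimate:** paired rate ratio (after/before) with 95% CI, for example Poisson GEE clustered by child with a small-sample-corrected robust variance. Another pre-specified paired count method would do. In the illustration with 40 children at 3 a year, GEE had 2-3 points more power than Wilcoxon but size of 5.3-6.5%, so it is offered for the interval rather than as the test.
- **Incomplete periods:** record months observed; use an offset in the rate ratio and the rate per 12 months in the Wilcoxon test. This arises if the dates in Section 3 bound the chart data, since a child who started before December 2012 would then have a short period before treatment.
- **Antibiotic outcome:** choose exacerbations or courses, and use that word in Sections 2, 3.1 and 6.
- **Hospitalisations:** state the source of the count in each period, reconciling chart review with HUQ.010.
- **Blanks:** the parent form tells parents who do not remember to leave the item empty; code these as missing, not zero.
- **Cox line:** state that it is not the before/after analysis of these endpoints.

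The cost is SAP wording and one extra item from charts already under review, with no extra patients or visits. The change does not remove before/after confounding.

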#### 4.2 INCLUSION CRITERIA

[Children and young people under 18 years old with Neuromuscular disease or with Cerebral Palsy treated with nebulised Hypertonic Saline for at least 12 months and their parents or legal guardians.]

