#### 4.3 EXCLUSION CRITERIA

[Children or young people who are also diagnosed with Cystic Fibrosis, as the effectiveness of nebulised Hypertonic Saline have already been studied extensively in this group.]

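### The uncontrolled before/after comparison has no specified recording or analysis of other respiratory care that changed around the start of saline, so any such effect would sit inside the saline estimate

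*Combined protocol and SAP*

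**What the plan says.** The effect comparisons use each child as his or her own control over time.

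- **Nocturnal outcomes** (section 6, Statistical Analysis Plan): Student t tests "comparing one year before and after starting treatment with Hypertonic Saline". Section 3.1 lists these outcomes among the primary endpoints; they include several SpO2 measures and "Oxygen desaturation index (ODI), Snoring and End tidal CO2 (EtCO2").
- **Antibiotics** (section 2, Secondary Objectives): the effect "on the number of courses of antibiotic prescribed compared to year before starting treatment".
- **Hospitalisations** (same section): whether saline "reduces the frequency of hospitalisations due to respiratory exacerbations compared to year before commencing treatment".
- **Lung function**, in the neuromuscular subgroup able to do spirometry (same section): to "assess whether the use of Hypertonic Saline decreases rate of decline of pulmonary function compared to year before commencing treatment".

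Section 4.2 admits children "treated with nebulised Hypertonic Saline for at least 12 months and their parents or legal guardians", so nobody is untreated. The only exclusion, in section 4.3, is "Children or young people who are also diagnosed with Cystic Fibrosis".

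In section 6, both count endpoints get a univariate chi-square test, and lung-function decline gets an independent t test and a Mann-Whitney test. The one model is a Cox model whose line breaks off after the word baseline and names no covariate. The section on assessment and follow-up is marked as not applicable, and there is no list of chart variables. The legible questionnaire items in Appendices 1 to 3 ask about usefulness, likes and difficulties, and sputum clearance. Appendix 1 also asks for counts of antibiotic courses and doctor visits in the 12 months before and after saline.

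**The concern.** Without a concurrent group, the change from one year to the next is the sum of everything that changed, not only saline. Sections 1.1 and 1.2 frame the question as effectiveness, with the hypothesis that saline reduces respiratory complications, so readers will take that change as the effect of saline.

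The population described in section 1.1 has weak cough, respiratory muscle fatigue, recurrent infection and possible respiratory failure. It is plausible that other respiratory care was adjusted in some of these children within a year of starting saline. The endpoints are exposed to such changes: ventilatory support acts on SpO2, the desaturation index and end-tidal CO2, and a change in long-term antibiotics bears on the count of antibiotic courses.

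If the dates of such changes are not abstracted, nobody can later say how many children were affected, or whether the result survives without them.

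**Working it through.** **1. Is there any provision in the plan?** Four places could contain one.

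- Control group: none. Sections 3 and 4.2 require at least 12 months on saline for everyone. The target of 40 for each group in section 6 is therefore not a treated-versus-untreated contrast.
- Recording: no outcome list, legible questionnaire item or chart-variable list covers other respiratory care. The antibiotic item in Appendix 1 is a yearly count of oral and intravenous courses; it does not date the start of long-term treatment.
- Eligibility: no restriction to children whose other care was stable.
- Analysis: univariate and two-sample tests, plus a Cox line with no named covariate.

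Section 7.2 asks for reasons to be recorded when a clinician gives alternative treatment, but only after study entry. Since 12 months of saline is an entry condition, the year before and the year after are already past by then.

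**2. How large could the effect be?** The plan gives no event rates, effect size, variance or co-treatment frequency, so no figure of its own can be reproduced. What follows is illustrative, and every input is an assumption: saline has no effect; a share p of children, 0.10 to 0.40, start another treatment; that treatment halves the event rate from its start.

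*All starts coincide with saline.* The year before is unaffected (relative rate 1) and starters run at 0.5 in the year after:

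ratio = 1 - 0.5p

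*Starts spread evenly from -12 to +12 months.* Half the starters begin before saline, on average midway through the year before. Their rates are 0.75 in that year and 0.5 in the next. The other half begin midway, on average, through the year after, with rates 1 and 0.75. The starters' means are (0.75 + 1)/2 = 0.875 before and (0.5 + 0.75)/2 = 0.625 after:

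ratio = (1 - 0.375p) / (1 - 0.125p)

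| p | All starts coincide | Starts spread evenly |
|---|---|---|
| 0.10 | 0.95 (fall 5%) | 0.9625/0.9875 = 0.975 (fall 2.5%) |
| 0.40 | 0.80 (fall 20%) | 0.85/0.95 = 0.895 (fall 10.5%) |

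**3. What would offset it?** Worsening natural history raises the second-year rate. The rise needed to cancel the falls above is the reciprocal of each ratio: 1/0.95 = 1.05 and 1/0.80 = 1.25 for coincident starts; 0.9875/0.9625 = 1.03 and 0.95/0.85 = 1.12 for spread starts. An underlying worsening of about 3% to 25% would hide the co-treatment effect, and a larger one would reverse the sign.

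**4. Could it produce a significant result?** A simulation used 40 paired before/after counts, a mean of 2 to 4 events per year, gamma-Poisson variation with shape 2, no saline effect, no underlying trend, and all co-treatment starting with saline. It used a two-sided 5% paired t test, which is not the chi-square test the plan names. The chance of a significant result favouring saline was about 2.5% with no co-treatment. It rose to 7% to 18% when 25% of children started other care and 15% to 56% when 50% did, over co-treatment rate ratios of 0.7 to 0.5. These are upper-end figures, because coincident starts are the worst timing.

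**The case against.** The strongest reply is that this is a generic limitation of any uncontrolled chart review, in a pilot whose primary objective is worded as exploratory. Several tempting stronger readings also fail.

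- A reader might infer that other care was in fact started with saline and that the estimate is therefore inflated. The documents nowhere say so. The objective on how parents "perceive the treatment with nebulised hypertonic saline compared to previous management" concerns perception only; it does not show what else changed, or when.
- A reader might infer that such care will not be recorded. The glossary mentions a case report form, but none is among the listed appendices, so one can say only that recording is not specified.
- A reader might infer that the Cox model cannot cope with care that changes over time. Cox models can take time-varying covariates. The line is incomplete, so the fair statement is that no covariate is named.
- A reader might infer that the bias must favour saline. Section 1.1 describes declining lung function in neuromuscular disease, which works against saline in a before/after comparison.
- A reader might infer that the nocturnal measures would shift more than the event counts. Nothing in the documents supports a size for that.

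These replies limit the claim but do not remove the gap. Unknown frequency is itself a reason to collect the dates, and a pilot is a good place to learn how common such changes are. The effectiveness wording in sections 1.1 and 1.2 also goes further than an exploratory aim.

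**Conclusion.** The gap is real. There is no control group, and the plan neither specifies recording other respiratory care nor analyses its changes, so any change within the two years would be folded into the saline estimate. Whether this happens, how often, and the net direction of bias cannot be determined from the documents.

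The 2.5% to 20% range in spurious reduction rests wholly on assumed shares, an assumed halving of event rates, two assumed timings, and no underlying trend. It shows that the issue could matter, not that it does. The point bears on how the result may be interpreted and should be settled before chart abstraction; it is not a reason to abandon the study.

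**What to change.** **Abstraction.** Add start and stop dates, from -12 to +12 months around the start of saline, for ventilatory support, mechanical airway-clearance devices and long-term antibiotics. Report how many children had a change and its timing relative to saline. State how long-term antibiotics are counted against the antibiotic-course endpoint.

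**Section 6.** Add a sensitivity analysis of each primary endpoint:

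- Where the data allow, a within-patient model with a before/after term and a time-varying indicator for co-treatment. This needs dated events from the charts, not only yearly questionnaire counts. It cannot separate the two effects in a child whose other care began exactly with saline.
- Otherwise, exclude children whose other care changed at or near the start of saline, with that interval defined before abstraction.
- Show separately any analysis that also excludes changes made later on saline, with the number excluded and a note that it selects on post-treatment events. Such changes may reflect deterioration on saline, and removing those children could flatter it.

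**Interpretation.** State that the pilot cannot attribute the before/after change to saline alone.

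**Cost.** A few extra fields from charts already being opened, and a smaller, less precise sensitivity sample: if 40% of a group of 40 were excluded, 40 - 16 = 24 would remain. Adding the fields after abstraction would mean reopening the charts.

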# 3. STUDY DESIGN

[Chart review of children and young people with Neuromuscular disease or with Cerebral Palsy who are cared for in the Royal Brompton Hospital and that have been treated with nebulised hypertonic saline for at least 12 months. Children and young people who are also diagnosed with Cystic Fibrosis will be excluded.

Parents or legal guardians will be asked to complete two questionnaires to further complement data from hospital records.

Participants between 10 and 18 years old will be asked to complete one questionnaire to complement hospital records.]

[Duration: 6 months.]

[We aim to review all charts of participants recruited that meet criteria between December 2011 and May 2018. We aim to recruit 40 participants from each group, including children, young people, and parents or legal guardians, as this will be a pilot study. Only participants recruited will have their charts reviewed]

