## 6. STATISTICS AND DATA ANALYSIS

[Sample Size:

We aim to recruit 40 participants for each group, including children and young people and their parents or legal guardians, as this is a pilot study.

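### The lung-function decline endpoint is assigned independent-sample tests, but its objective compares the same children before and after starting treatment

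*Combined protocol and SAP*

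**What the plan says.** - **Test named.** The Statistical Analysis Plan in Section 6 gives this endpoint one line: "Independent t testing and Mann-Whitney U test to analyse *Rate of decline in pulmonary function". It does not say which two sets of slopes are compared.
- **Objective.** Section 2, Secondary Objectives, sets the question: "assess whether the use of Hypertonic Saline decreases rate of decline of pulmonary function compared to year before commencing treatment". It limits the question to one population: "In the subgroup of participants with neuromuscular disease who can perform spirometry".
- **Status.** Section 3.1 lists "Rate of decline of pulmonary function" under Primary Endpoints, although Section 2 places the objective among the secondary ones.
- **Who supplies data.** Section 4.2 admits children "treated with nebulised Hypertonic Saline for at least 12 months", and Section 3 adds "Only participants recruited will have their charts reviewed".
- **Neighbouring line.** For nocturnal outcomes, Section 6 does state the contrast: "comparing one year before and after starting treatment with Hypertonic Saline". It does not say whether that t test is paired.
- **Size.** Section 6 says "We aim to recruit 40 participants for each group, including children and young people and their parents or legal guardians". It does not make clear who the 40 are, and it gives no number able to perform spirometry.

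**The concern.** The independent t test and the Mann-Whitney U test both assume that the two samples come from different, unrelated people. Here each child in the spirometry subgroup contributes a slope for the year before treatment and a slope for the time on it. No paired t test, signed-rank test or repeated-measures model is named anywhere in the plan.

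An analyst who follows the line literally would get the standard error wrong whenever a child's two slopes are correlated. With negative correlation the P value is too small. With positive correlation it is too large, and a real slowing of decline is easier to miss. What is at stake is whether a listed primary endpoint has any valid test of its own objective.

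**Working it through.** **1. Is there a second, unrelated sample?** The plan offers no such sample for this objective.

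- Untreated children: none. Section 4.2 requires at least 12 months of treatment, and Section 3 restricts chart review to recruited participants.
- Neuromuscular disease against cerebral palsy: excluded, because Section 2 restricts this objective to neuromuscular disease.
- 3% against 7%: both concentrations are named in Section 2, but no objective compares them. If that was the intended contrast, the before/after objective has no analysis.
- The Cox line in Section 6 concerns differences by baseline and does not supply a before/after comparison of slopes.

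**2. Effect of ignoring the pairing.** The plan gives no power-based figure to reproduce. Let n children each have two slopes with common SD σ and within-child correlation ρ. The independent formula takes the variance of the mean difference as 2σ²/n. The true variance is 2σ²(1-ρ)/n. The ratio is 1/(1-ρ): 0.67, 0.80, 1.00, 1.33 and 2.00 for ρ = -0.5, -0.25, 0, +0.25 and +0.5. In large samples the true type I error of a nominal 5% test is 2Φ(-1.96/√(1-ρ)). At ρ = -0.5 this is 2Φ(-1.60) ≈ 0.11, and at ρ = +0.5 it is 2Φ(-2.77) ≈ 0.006.

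**3. Small-sample check.** All ρ, n and effect sizes below are assumptions. Slopes were simulated as bivariate normal with unit SD and tested two-sided at 5%, with 100,000 replicates per cell for t tests and 50,000 for rank tests.

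Type I error, n = 10 / 20 / 40:

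| ρ | Independent t | Mann-Whitney U |
|---|---|---|
| -0.5 | 0.107 / 0.109 / 0.109 | 0.094 / 0.105 / 0.102 |
| -0.25 | 0.077 / 0.079 / 0.080 | 0.066 / 0.074 / 0.074 |
| 0 | 0.050 / 0.049 / 0.050 | 0.042 / 0.051 / 0.048 |
| +0.25 | 0.028 / 0.025 / 0.025 | 0.024 / 0.026 / 0.024 |
| +0.5 | 0.009 / 0.007 / 0.006 | 0.009 / 0.009 / 0.008 |

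The paired t test stays at 0.049-0.051 and the signed-rank test at 0.047-0.049 throughout.

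Power (%) for a change of 0.5 SD of the yearly slope, independent t (simulated) v paired t (noncentral t, noncentrality 0.5√n/√(2(1-ρ))):

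| ρ | n = 10 | n = 20 | n = 40 |
|---|---|---|---|
| -0.5 | 23.7 v 13.0 | 37.0 v 23.2 | 58.2 v 42.9 |
| -0.25 | 21.2 v 14.6 | 35.5 v 26.9 | 58.9 v 49.6 |
| 0 | 18.6 v 17.1 | 33.8 v 32.4 | 60.1 v 58.7 |
| +0.25 | 15.5 v 21.2 | 31.3 v 41.1 | 61.4 v 71.2 |
| +0.5 | 11.9 v 29.3 | 28.7 v 56.5 | 63.5 v 86.9 |

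At negative ρ the independent test's higher figure reflects its excess type I error. It is not a genuine gain.

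**4. What could set ρ?** Take slopes from two readings a year apart. Let k be the true slope variance divided by the reading-error variance, and c the correlation of a child's true slopes in the two years. If the start-of-treatment reading serves both slopes, its error enters with opposite signs and ρ = (ck-1)/(k+2). If it does not, ρ = ck/(k+2).

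- Shared reading, c = 1, k = 0, 1, 4: ρ = -0.50, 0, +0.50.
- Separate readings, c = 1, k = 0, 1, 4: ρ = 0, +0.33, +0.67.

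Either sign is possible. The value -0.5 needs a shared reading and no true variation in slope.

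**The case against.** Four points can be made for the plan.

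- **The line names no contrast.** The investigators may have had some independent grouping within the neuromuscular subgroup in mind, and the tests could be valid for it. That is possible, but the before/after objective would then have no test at all. The mismatch stands on either reading; only its mechanism changes.
- **Pairing may be incomplete.** Section 4.2 requires no spirometry in the year before treatment, so some children may have only an after slope. Assume 10 complete pairs plus 10 after-only children and a 0.5 SD change. Power, independent v paired, is then about 24% v 17% at ρ = 0, 22% v 21% at +0.25 and 20% v 29% at +0.5. This stands as a real cost of a strictly paired analysis. It does not make the unpaired test valid when ρ is not 0.
- **The harm is not demonstrated.** Correlation, subgroup size and effect size are all assumed, and some plausible settings give ρ = 0 and no error. This is correct, so the concern rests on the mismatch and not on a proven bias.
- **This is an exploratory pilot.** Its pilot status can excuse the absence of a power calculation. It does not excuse a test for a different data structure on a listed primary endpoint, when the correction needs only wording.

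**Conclusion.** The concern holds, and the line should be corrected before analysis. Within the plan's own design, the before and after rates of decline come from the same treated children, and the tests named are for unrelated samples. That conclusion follows from the documents and needs no assumed figure.

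The size of the error does depend on assumptions. For ρ between -0.5 and +0.5, the independent t test's type I error is about 11% at one end and 0.6-0.9% at the other. With complete pairs, the paired t test is 1-2 points less powerful at ρ = 0, 6-10 points more powerful at +0.25 and 17-28 points more powerful at +0.5. The direction of error in this study cannot be determined from the documents.

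**What to change.** Replace the Section 6 line with text such as:

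> In participants with neuromuscular disease who can perform spirometry, a rate of decline of [named measure and unit] will be calculated for each child for the 12 months before and the first 12 months after starting hypertonic saline, from at least [number] readings per period. The within-child difference will be analysed by paired t test, with the Wilcoxon signed-rank test as a check, and reported as a mean difference with 95% CI and the number of children contributing.

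The investigators should also:

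- confirm the 12-month window after starting, which is inferred from Section 4.2 and the nocturnal-outcomes line because the objective does not state one;
- say whether the start-of-treatment reading enters both slopes;
- report any 3% v 7% comparison separately, with its own stated objective;
- record as a limitation that children are older in the treated year and that regression to the mean is possible, so slower decline cannot be credited to treatment alone. Section 1.1 itself says FVC falls faster at younger ages, and pairing does not remove this.

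A mixed model of the spirometry readings could be added as a sensitivity analysis and could use children with readings in only one period. It should include a fixed change in slope at treatment start (the effect of interest), age, and child-level random slope and random change in slope. It may not be estimable in a small subgroup.

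The cost is SAP wording only. Children without a slope in both years leave the paired analysis, in a number the documents do not allow us to estimate. The 1-2 point loss of power at ρ = 0 applies to complete pairs; with many after-only children it is larger, about 7 points in the example above (24% v 17%).
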